### **9.1 Laboratory Correlative Studies Sample Processing**

Instructions for handling, preserving, and shipping the specimens are described in the Lab Manual.

## **10 MEASUREMENT OF EFFECT**

All baseline evaluations will be performed as closely as possible to the beginning of treatment. For subsequent evaluations, the method of assessment and techniques will be the same as those used at baseline.

### **10.1 Response Criteria**

In order to evaluate efficacy, all study-required tumor assessments and PSA measurements must be obtained. Baseline and all post baseline PSA assessments will be used to measure PSA response rate and time to PSA progression based on protocol-specific/modified PCWG3 criteria. Any unscheduled PSA measurement will be included in the periodic assessment of PSA progression.

Radiographic scans (CT, MRI, or bone) will be used to assess best overall response and radiographic progression based on PCWG–modified RECIST criteria for soft-tissue lesions and protocol-specific criteria for bone lesions. Baseline images should be taken during Screening as close as possible to, and never more than 28 days before, Day 1 Week 1. Every effort must be made to ensure the same radiographic method is used before and after treatment at scheduled visits.

Other disease-related signs or symptoms suggestive of progression, including escalating pain not referable to another cause, increased LFT in subjects with baseline liver metastases, increased ascites, declining performance status, and examination findings consistent with disease progression, are valid reasons to consider an unscheduled assessment of tumor status.

### **10.2 Measurable soft-tissue lesions**

When evaluating soft-tissue lesions, the following PCWG-modified RECIST response criteria for target(soft-tissue) lesions definitions apply.

- Complete response (CR): the disappearance of clinical and radiological evidence of all target lesions and normalization of tumor marker levels
- Partial response (PR): a decrease from baseline  $\geq 30\%$  in the sum of the LD of all target lesions
- Progressive disease (PD): an increase  $\geq 20\%$  in the sum of the LD of all target lesions based on the smallest sum LD since treatment started or the appearance of one or more new lesions or the appearance of new lesions
- Stable disease (SD) : neither sufficient shrinkage to qualify for PR nor sufficient increase to qualify for PD based on the smallest sum LD recorded since treatment started

### 10.3 PSA

As long as patient safety is the primary concern, in the absence of other indicators of disease progression, therapy should not be discontinued solely on the basis of a rise in PSA.

For each patient, a waterfall plot will be used to report the percent change in PSA from baseline to 12 weeks (or earlier for those who discontinue therapy) and the maximum decline in PSA that occurs at any point after treatment

### 10.4 Bone

Record post-treatment changes as either “no new lesions” or “new lesions”. In the absence of clearly worsening soft-tissue (nodal and visceral) disease or disease-related symptoms, progression at the first scheduled assessment should be confirmed on a second scan performed 6 or more weeks later. In the rare case where visible lesions disappear, this too should be confirmed.

### 10.5 Duration of Response

#### Duration of overall response:

Duration of overall response is measured from the time when partial response or complete response is first noted until the date when recurrent or progressive disease is objectively documented. Duration of overall complete response is measured from the time the criteria for complete response are first met until the first date that recurrent disease is objectively documented. Duration of stable disease is measured from the start of treatment until the criteria for progression are met.

### 10.6 Progression-Free Survival

Radiographic progression will be assessed as per PCWG3 criteria. Radiographic progression-free survival (rPFS) is a composite endpoint defined as the time from treatment start to disease progression in bone or soft-tissue, or death, whichever occurs first. All assessments of disease should be collected at the same time interval (e.g., bone scan, CT scan, and PSA). In addition to PSA, confirm post-treatment changes in measurable target lesions, radionuclide bone scans, and symptoms.

## 11. DATA REPORTING / REGULATORY CONSIDERATIONS

### 11.1 Data Collection

The data collection plan for this study is to utilize REDCap Cloud to capture all treatment, toxicity,

efficacy, and adverse event data for all enrolled subjects.

#### **11.1.1 REDCap Cloud**

REDCap Cloud is a secure web-based commercial grade electronic data capture (EDC) and management system that is 21 CFR Part 11 compliant and HIPAA compliant. It is also HITRUST and ISO27001 certified. The REDCap Cloud platform extends the features of academic REDCap to create a regulatory-compliant application with features suitable for building and managing projects ranging from online surveys and databases through Phase III clinical trials.

### **11.2 Regulatory Considerations**

#### **11.2.1 Institutional Review Board/Ethics Committee Approval**

As required by local regulations, the Investigator will ensure all legal aspects are covered, and approval of the appropriate regulatory bodies obtained before study initiation.

Before initiation of the study at each study center, the protocol, the ICF, other written material given to the patients, and any other relevant study documentation will be submitted to the appropriate Ethics Committee. Written approval of the study and all relevant study information must be obtained before the study center can be initiated or the IP is released to the Investigator. Any necessary extensions or renewals of IRB approval must be obtained for changes to the study, such as amendments to the protocol, the ICF, or other study documentation. The written approval of the IRB together with the approved ICF must be filed in the study files.

The Investigator will report promptly to the IRB any new information that may adversely affect the safety of the patients or the conduct of the study. The Investigator will submit written summaries of the study status to the IRB as required. On completion of the study, the IRB will be notified that the study has ended.

All agreed protocol amendments will be clearly recorded on a protocol amendment form and will be signed and dated by the original protocol approving signatories. All protocol amendments will be submitted to the relevant institutional IRB for approval before implementation, as required by local regulations. The only exception will be when the amendment is necessary to eliminate an immediate hazard to the trial participants. In this case, the necessary action will be taken first, with the relevant protocol amendment following shortly thereafter.

All protocol amendments and consent form modifications will be made by the Principal Investigator. Exelixis will have the opportunity to review and approve the changes prior to submission of these changes to the local IRB and distribution to participating sites.

Once protocol amendments or consent form modifications are implemented at the lead site, Weill Cornell Medicine, updated documents will be provided to participating sites, as applicable. Weill Cornell Medicine must approve all consent form changes prior to local IRB submission.

Relevant study documentation will be submitted to the regulatory authorities of the participating countries, according to local/national requirements, for review and approval before the beginning of the study. On completion of the study, the regulatory authorities will be notified that the study has ended.

#### **11.2.2 Ethical Conduct of the Study**

The Investigators and all parties involved should conduct this study in adherence to the ethical principles based on the Declaration of Helsinki, GCP, ICH guidelines and the applicable national and

local laws and regulatory requirements.

This study will be conducted under a protocol reviewed and approved by the applicable ethics committees and investigations will be undertaken by scientifically and medically qualified persons, where the benefits of the study are in proportion to the risks.

#### **11.2.3 Informed Consent**

The investigator or qualified designee must obtain documented consent according to ICH-GCP and local regulations, as applicable, from each potential subject or each subject's legally authorized representative prior to participating in the research study. Subjects who agree to participate will sign the approved informed consent form and will be provided a copy of the signed document.

The initial ICF, any subsequent revised written ICF and any written information provided to the subject must be approved by IRB prior to use. The ICF will adhere to IRB requirements, applicable laws and regulations.

#### **11.2.4 Compliance with Trial Registration and Results Posting Requirements**

Under the terms of the Food and Drug Administration Modernization Act (FDAMA) and the Food and Drug Administration Amendments Act (FDAAA), the Sponsor-Investigator of the trial is solely responsible for determining whether the trial and its results are subject to the requirements for submission to <http://www.clinicaltrials.gov>. Information posted will allow subjects to identify potentially appropriate trials for their disease conditions and pursue participation by calling a central contact number for further information on appropriate trial locations and trial site contact information.

#### **11.2.5 Record Retention**

Essential documents are those documents that individually and collectively permit evaluation of the study and quality of the data produced. After completion of the study, all documents and data relating to the study will be kept in an orderly manner by the Investigator in a secure study file. Essential documents

should be retained for 2 years after the final marketing approval in an ICH region or for at least 2 years since the discontinuation of clinical development of the IP. In addition, all subjects' medical records and other source documentation will be kept for the maximum time permitted by the hospital, institution, or medical practice.

## **12. STATISTICAL CONSIDERATIONS**

The proposed design is a single-arm, open-label, non-randomized study. The primary endpoint is radiographic progression-free survival (rPFS) defined as the time from initiation of treatment to minimum of radiographic progression or death, whichever occurs first. The historical control of median rPFS of 5.6 months (from COMET-1) would approximately translate to a 50% rPFS rate at 6 months.

The entire cohort as well as subgroup analysis by specific genomic alterations will be performed.

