#### 4.4 Molecular Eligibility

To be eligible, a patient's tumor must have evidence of gene amplification, an activating mutation, or overexpression of one of the following genes: MET, KIT, RET, VEGFR-1, VEGFR-2, VEGFR-3, FLT3, AXL, TRKB, or TIE2. In the event of activating mutations, the observed mutation must be of Level 1, Level 2, or Level 3 as annotated by OncoKB ([www.oncokb.org](http://www.oncokb.org)). Eligibility can be met by **at least one** of the following diagnostic tests:

- 1) DNA sequencing of a metastatic tumor biopsy specimen showing gene amplification or activating mutation using a CLIA-certified assay. Tumor tissue samples must have been collected within 6 months of enrollment.
- 2) Protein overexpression in a metastatic tumor biopsy specimen determined by immunohistochemistry (IHC) showing 3+ protein expression using a CLIA-certified assay. These

- include common in-house KIT and commercial reference labs for panTRK (*e.g.* NeoGenomics) and cMET (*e.g.* NeoGenomics, Caris, Mayo Clinic).
- 3) CLIA-certified commercial cell free DNA assay (either Guardant360 or FoundationOneLiquid assay) reporting gene amplification or activating mutation *within 6 months of enrollment*.
    - a. For the Guardant360 Liquid Biopsy amplification must be at least (++) or (+++) for to meet eligibility.
    - b. For the FoundationOneLiquid assay, amplification will be eligible. Reports that have an “equivocal” or “subclonal” designation will not be eligible.
  - 4) Any non-CLIA certified assay such as RNA expression profiling of a metastatic tumor biopsy specimen showing overexpression must be confirmed by a CLIA-certified assay (*i.e.*, immunohistochemistry showing 3+ protein expression)

Patients who do not meet molecular eligibility criteria will be allowed to enroll if they have liver metastases that meet RECIST criteria for measurable disease. Patients with prostate adenocarcinoma or NEPC will be allowed to enroll.

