### **12.1 Study Design/Endpoints**

The proposed design is a single-arm, open-label, non-randomized study. The primary endpoint is radiographic progression-free survival (rPFS) defined as the time from initiation of treatment to minimum of radiographic progression or death, whichever occurs first. We will enroll up to 28 patients with liver metastasis aimed to estimate the rPFS survival probabilities. Using the Kaplan-Meier estimator, with this sample size, we estimate the 95% CI of the median survival probability is 31.1-68.9%

Secondary endpoints include PSA decline, tumor response, and OS.

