## **12.2 Sample Size/Accrual Rate**

Sample size for the entire trial will be 30 patients. Accrual will not mandate an equal number of each of the qualifying molecular abnormalities. The sponsor retains the right to terminate enrollment in any specific genetic alteration if no significant benefit is observed in that given cohort.

Any enrolled subject who withdraws for any reason prior to a full 28 days of treatment and assuming he did undergo the second biopsy ("on treatment biopsy") will be replaced and not incorporated into the analysis.

Accrual is anticipated to be 1-4 patients per month in total across all study sites

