## **12.3 Analysis of Endpoints**

### ***12.3.1 Analysis of Primary Endpoints***

Median rPFS will be estimated using Kaplan-Meier methodology. Greenwood's formula will be used to calculate 95% CIs for the Kaplan-Meier estimates.

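### Radiographic PFS by genomic alteration would be estimated in subgroups of about 1-5 patients, where the only interval method the plan states (Greenwood) is invalid

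*Combined protocol and SAP*

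**What the plan says.** Section 12 defines the primary endpoint, rPFS, and translates the historical median of 5.6 months into roughly 50% progression-free at 6 months. It then states: "The entire cohort as well as subgroup analysis by specific genomic alterations will be performed". That sentence gives no list of subgroups, minimum size, interval method or status.

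The numbers available to those subgroups come from four places:

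- Section 4.4 names ten qualifying genes: "MET, KIT, RET, VEGFR-1, VEGFR-2, VEGFR-3, FLT3, AXL, TRKB, or TIE2".
- Section 12.2: "Sample size for the entire trial will be 30 patients", and "Accrual will not mandate an equal number of each of the qualifying molecular abnormalities".
- Section 12.1: "We will enroll up to 28 patients with liver metastasis aimed to estimate the rPFS survival probabilities".
- Section 4.4 waives the molecular requirement for measurable liver disease: "Patients who do not meet molecular eligibility criteria will be allowed to enroll if they have liver metastases".

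On method, Section 12.3.1 says that Greenwood's "formula will be used to calculate 95% CIs for the Kaplan-Meier estimates". No other interval for rPFS appears.

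On accrual, Section 12.2 says: "The sponsor retains the right to terminate enrollment in any specific genetic alteration if no significant benefit is observed in that given cohort". Significant benefit is not defined there. Section 3.1 has a separate numeric rule: accrual for an alteration may close if at least 6 of 12 patients with it progress before 6 months. Neither section refers to the other.

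Two places bear on status. Section 1.2.3 lists the relation between tumor genomic abnormalities and antitumor activity as an exploratory objective. Section 12.4, on exploratory endpoints, contains log-rank comparisons between subgroups, and a Benjamini-Hochberg procedure limited to genomic measurements.

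**The concern.** Greenwood's variance is a large-sample formula. In a subgroup of two or three patients who all remain progression-free at 6 months, the Kaplan-Meier estimate is 1 and the variance is 0. The printed interval is then 100% to 100%, or missing, depending on software. A result carrying almost no information would look perfectly precise and would appear to exclude the 50% reference stated in the same section.

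This matters because Section 2.3 predicts that molecular selection will identify the patients who benefit most. Readers will look for per-alteration rPFS and carry it into the design of later trials. The accrual right in Section 12.2 also looks to benefit within a single alteration, where almost no information will exist.

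**Working it through.** **The plan's own interval.** Without censoring, Greenwood's interval for a survival probability p is p ± 1.96 × √(p(1 − p)/n). Section 12.1 quotes 31.1-68.9% for up to 28 patients.

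- n = 28: 0.5 ± 1.96 × √(0.25/28) = 31.5-68.5%.
- n = 27 (or n = 28 with n − 1 in the variance): 0.5 ± 1.96 × √(0.25/27) = 31.1-68.9%, which matches.
- A log-log interval at n = 28 gives 30.6-66.6%, which does not match.

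So the plan's figure is of the plain Greenwood type, and that type is used below.

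**Subgroup size.** If all 30 patients had exactly one alteration, the average would be 30/10 = 3 per gene. A lower setting: Section 2.3 gives about 17% prevalence in an mCRPC cohort. Applying this to liver patients is an assumption. It gives 0.17 × 28 = 4.8 altered liver patients, plus 2 non-liver patients who must be altered, so about 7 over ten genes.

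**One subgroup.** Assume a true 6-month rate of 50% and complete follow-up. The table sums the binomial probabilities of all results whose lower limit exceeds 50%. The exact lower limit when all n are progression-free is 0.025^(1/n).

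| n | Results with Greenwood lower limit > 50% | Probability | Exact lower limit for n/n | Exact-method probability |
|---|---|---|---|---|
| 2 | 2/2 | 1/4 = 25% | 15.8% | 0% |
| 3 | 3/3 | 1/8 = 12.5% | 29.2% | 0% |
| 4 | 4/4 | 1/16 = 6.3% | 39.8% | 0% |
| 5 | 5/5 | 1/32 = 3.1% | 47.8% | 0% |
| 6 | 5/6, 6/6 | 7/64 = 10.9% | 54.1% | 1/64 = 1.6% |

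The nominal rate is 2.5%. At n = 6, 5/6 counts because 0.833 − 1.96 × √(0.833 × 0.167/6) = 0.535. Censoring does not repair the collapse: any subgroup without an event before 6 months has an estimate of 1 and zero variance.

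**At least one subgroup.** Altered patients are spread at random over ten equally likely genes, with a true rate of 50% in each (simulation).

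| Altered patients | Subgroups of 2 or more counted | Subgroups of 3 or more counted |
|---|---|---|
| 7 | 31% | 3% |
| 12 | 53% | 12% |
| 30 | 68% | 41% |

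If subgroups in which everyone is progression-free are excluded, the figures are 0% with 7, about 0.1% with 12 and about 6% with 30. With exact limits (subgroups of 2 or more) they are 1% or less.

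**The two accrual statements.** With all 30 patients altered and spread evenly at random, the chance that any gene reaches 12 patients is about 10 × P(Binomial(30, 0.1) ≥ 12) = 10 × 0.0000153 = 0.015%. The Section 3.1 rule would almost never become usable. For Section 12.2, no exact 95% interval can exclude 50% from below with 5 or fewer patients, since even 5/5 has a lower limit of 47.8%.

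**The case against.** The strongest reply is that the plan is an estimation plan. It states no alpha, test or success threshold, for the cohort or for any alteration; 50% is historical context. The use of Greenwood limits within subgroups is inferred. The exploratory label exists, in Section 1.2.3 and in the heading of Section 12.4, and is absent only from one sentence in Section 12. All of this is correct. A reader might infer that the plan treats per-alteration rPFS as confirmatory; the documents do not say so.

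A reader might also infer that a false active alteration is likely. That is not supported. The higher figures come almost wholly from 2/2 and 3/3 results with zero-width intervals, and they fall to about 3% with 7 altered patients and a minimum size of 3.

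Nor do the documents support reading Section 12.2 as a right triggered whatever the drug does. Significant benefit is undefined, the protocol elsewhere uses the word significant in a non-statistical sense, and the right is discretionary. It permits closure for lack of benefit, so its main risk is early closure of an active alteration rather than a false claim of activity.

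What remains is the interval. Neither exploratory passage refers to the Section 12 analysis or supplies an rPFS interval for it, and an exploratory label would not make a zero-width interval correct.

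**Conclusion.** The point holds as a defect of method in very small subgroups. If the stated Greenwood limits are applied by alteration, a subgroup of 2 to 4 patients would show a lower limit above 50% in 25% to 6.3% of cases when the true rate is 50%, against 2.5% nominal. The rate is 3.1% at n = 5 and 10.9% at n = 6. These figures assume complete follow-up to 6 months and plain Greenwood limits.

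The trial-wide figure is not fixed by the documents. With ten equally likely genes it runs from about 3% to 68%, depending on how many patients carry an alteration and on the smallest subgroup reported. Because no subgroup threshold is set, these are rates of misleading intervals, not the error rate of a planned test.

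Separately, the accrual statements in Sections 12.2 and 3.1 are unreconciled. One is undefined, and the other needs a subgroup size that 30 patients will almost never supply.

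**What to change.** In Section 12, state that per-alteration rPFS results belong to the exploratory analyses and support no efficacy claim.

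For each alteration, and for any stratum too small for Greenwood limits, report n, the number progression-free at 6 months with an exact (Clopper-Pearson) interval where follow-up is complete, and the individual times. This includes the non-liver stratum, which could hold as few as 2 patients (30 − 28). Keep Kaplan-Meier with Greenwood limits for the entire cohort and the larger liver stratum.

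Reconcile the accrual right in Section 12.2 with the 6-of-12 rule in Section 3.1, so that the plan has one defined basis, or an explicit cross-reference, for closing an alteration.

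The cost is a few sentences and slightly simpler tables. The downside is that no single-alteration efficacy claim can be made, which these numbers could not support anyway.

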### **12.1 Study Design/Endpoints**

The proposed design is a single-arm, open-label, non-randomized study. The primary endpoint is radiographic progression-free survival (rPFS) defined as the time from initiation of treatment to minimum of radiographic progression or death, whichever occurs first. We will enroll up to 28 patients with liver metastasis aimed to estimate the rPFS survival probabilities. Using the Kaplan-Meier estimator, with this sample size, we estimate the 95% CI of the median survival probability is 31.1-68.9%

Secondary endpoints include PSA decline, tumor response, and OS.

## **12.2 Sample Size/Accrual Rate**

Sample size for the entire trial will be 30 patients. Accrual will not mandate an equal number of each of the qualifying molecular abnormalities. The sponsor retains the right to terminate enrollment in any specific genetic alteration if no significant benefit is observed in that given cohort.

Any enrolled subject who withdraws for any reason prior to a full 28 days of treatment and assuming he did undergo the second biopsy ("on treatment biopsy") will be replaced and not incorporated into the analysis.

Accrual is anticipated to be 1-4 patients per month in total across all study sites

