## 1. PROTOCOL SUMMARY

Full Title	Open Label Phase II Trial of Cabozantinib in Patients with Metastatic Castrate Resistant Prostate Cancer (mCRPC) and Known Amplifications or Activating Mutations in Gene Targets of Cabozantinib or Liver Metastases who have Received Prior Anti-Androgen Therapy
Short Title	Cabozantinib for mCRPC
Clinical Phase	Phase 2
Principal Investigator	[name]
Sample Size	N = 30
Accrual Ceiling	Enroll up to 30 subjects and screen up to 100 subjects
Study Population	Men with CRPC who have progressed on a second-line anti-androgen therapy
Accrual Period	24 months
Study Design	
This is a phase II non-randomized, open label trial designed to evaluate treatment response and survival of patients with mCRPC who harbor evidence of increased signaling (via evidence of DNA amplification or RNA overexpression) of the targets of cabozantinib (MET, KIT, RET, VEGFR-1 (FLT1), VEGFR-2 (KDR), VEGFR-3 (FLT4), FLT3, AXL, TRKB, and TIE2) or who have or liver metastases.
 
All patients will receive cabozantinib at 40 mg/day. Dose reduction (from 40 to 20 mg and to 20 mg every other day) or interruptions of treatment will be allowed for unacceptable adverse events (AEs).

Study Duration	Approximately 12 months after enrollment, then patients will shift to long-term follow up
Study Agent	Cabozantinib, 40 mg PO daily
Primary Objective	To assess the radiographic response proportion of cabozantinib in patients with metastatic CRPC who have progressed on an androgen receptor signalinginhibitor whose tumor possess a molecular abnormality that is targeted by cabozantinib or who have liver metastases
Secondary Objectives	
 
• To assess PSA decline by PCWG3
 
• To measure overall survival (OS)
 

Exploratory Objectives	
 
• To explore prognostic and/or predictive biomarkers of cabozantinib in whole blood, plasma and tumor samples: 
 
○ To evaluate for and measure changes in targeted genes found in cell-free DNA at baseline, in response to treatment, and at the time of disease progression
 
○ To explore the effects of cabozantinib on
 
 
 

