 cfDNA, circulating immune activity, lipase can be collected within 30 days prior to C1D1 or pre-dose C1D1

 When plasma DNA is collected, it should be collected as close to biopsy date as possible, including same day. In the event it is collected on the same day, the specimen should be acquired *prior* to the biopsy procedure.

 Every 12 weeks (± 5 days) until disease progression. For EOT, does not have to be repeated if done within 6 weeks of visit.

 Assess continuously until disease progression

 Every 12 weeks beginning with C4D1 (e.g. C4, C7, C10, etc).

 Collect only on C4D1

 Pre-treatment biopsy can be waived provided that adequate archival material for molecular analyses available from biopsy performed within 3 months of enrollment

 On-treatment biopsy during cycle 1 after 3 weeks of therapy. Biopsy must be performed between day 21 and day 24 on therapy (inclusive). *NB: cabozantinib must be held 5 days before and 5 days after biopsy*

Cycle = 28 days	Screening	Cycle 1			Cycle 2	Cycle 3	Cycle 4 +	End of Treatment	Survival Follow-Up
	Day -30 to -1	Day 1	Day 14	Day 21 (+ 3 days)	Day 1 (± 3 days)	Day 1 (± 3 days)	Day 1 (± 3 days)	Post-Treatment	
Concomitant medications 	X	X			X	X	X	X	
Adverse events 	X	X	X		X	X	X	X	
Health Care Resources 	X	X			X	X	X	X	
Cabozantinib dosing 		X			X	X	X		
Dispense/return of oral study drug and compliance accounting		X			X	X	X	X	
Additional cancer treatment, survival status								X	Subjects will be followed every 12 weeks for 2 years after completion of the study or until death, whichever occurs first

 Document those taken from 30 days prior to treatment through 30 days after the decision to discontinue study treatment

 Document new or worsening events from time of informed consent through 30 days after the last dose of study treatment (related SAEs at any time). Adverse events information will be collected at study visits and may also be collected at any time over the phone or by spontaneous subject report. At study visits where any study treatment is administered, adverse events will be documented pre- and post-dose. Certain AEs and all SAEs that are ongoing 30 days after last dose of study treatment are to be followed until resolution or determination by the investigator that the event is table or irreversible.

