### ***12.3.2 Analysis of Secondary Endpoints***

The median OS will be estimated using Kaplan-Meier methodology. Greenwood's formula will be used to calculate 95% CIs for the Kaplan-Meier estimates. The proportion of men with a meaningful decrease in PSA from baseline (30% and 50% declines will both be used) will be summarized with a binomial point estimate and corresponding 95% binomial CI. Likewise, the proportion of patients with a tumor response (modified RECIST response of CR or PR) will also be estimated with a binomial point estimate and 95% CI.

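### Section 12.2 drops some treated men from the analysis for withdrawing after first dose, under a biopsy condition that appears inverted; any bias in rPFS and OS is upward, with a size that depends on the reading

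*Combined protocol and SAP*

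**What the plan says.** Section 12.2 sets the rule. It covers "Any enrolled subject who withdraws for any reason prior to a full 28 days of treatment", and continues: "and assuming he did undergo the second biopsy ('on treatment biopsy') will be replaced and not incorporated into the analysis". No endpoint is named, so the exclusion reaches every analysis. The plan defines no all-treated set and no sensitivity analysis.

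Other parts of the plan bear on it:

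- Section 12.1 gives rPFS as "defined as the time from initiation of treatment to minimum of radiographic progression or death, whichever occurs first"; Sections 10.6 and 12 agree.
- For OS, Section 12.3.2 says "The median OS will be estimated using Kaplan-Meier methodology", but states no time origin. Section 12.4 mentions a clock starting at baseline only for exploratory models.
- Section 12 supplies the comparison: "The historical control of median rPFS of 5.6 months (from COMET-1) would approximately translate to a 50% rPFS rate at 6 months".
- The second biopsy falls on days 21 to 24 (Section 6.1, footnote 11; Section 6.5). First scheduled on-treatment imaging is at 12 weeks (Section 6.1, footnote 6).
- Section 12.5.1 limits toxicity evaluation to men with at least 4 weeks of drug, and Section 12.5.2 limits response assessment to men with at least 3 cycles.
- The Protocol Summary sets the accrual ceiling: "Enroll up to 30 subjects and screen up to 100 subjects".

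**The concern.** A man's membership of the analysis set is decided by something that happens after his rPFS clock has started. Withdrawal for any reason includes toxicity and clinical deterioration, and such men are likelier than average to progress or die early. Removing them leaves a set partly selected for having lasted. With one arm there is no control group to share the bias, and the documents describe no matching exclusion in COMET-1.

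The biopsy condition makes the rule hard to apply. A replacement rule meant to protect the paired-biopsy studies would replace men who did **not** have the second biopsy. This one replaces men who did, and does not say what happens to the others. *Withdraws* is also undefined: it could mean leaving treatment or leaving the study, and the text does not say whether death or progression counts.

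Finally, a replaced man has already been enrolled. Once anyone is replaced, 30 analysed men cannot be reached within a ceiling of 30 enrolled.

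**Working it through.** **Inputs.** From the documents: median rPFS 5.6 months and median OS 11.0 months (COMET-1, cabozantinib arm); biopsy on days 21–24; cut-off at 28 days; N = 30. Assumed: exponential times, 30.4375 days per month, every early failure dropped, and days counted as calendar days. The documents give no early-withdrawal rate.

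**The plan's own figures.** The stated 95% CI of 31.1–68.9% around 50% comes from 0.5 ± 1.96 × √(0.25/n). n = 27 gives 31.1–68.9%; the stated n = 28 gives 31.5–68.5%, close enough. For the benchmark, S(6) = 0.5^(6/5.6) = 47.6%, which the plan rounds to about 50%.

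**Formula.** If a share d of treated men is dropped and all of them would have failed by 6 months, reported S(6) = 47.6% / (1 − d).

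**Survival at the relevant days.** Days 21, 24 and 28 are 0.690, 0.789 and 0.920 months.

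- S(day 21) = 0.5^(0.690/5.6) = 0.918
- S(day 24) = 0.5^(0.789/5.6) = 0.907
- S(day 28) = 0.5^(0.920/5.6) = 0.892

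| Reading | Men dropped | d | Reported S(6) | Median (months) |
|---|---|---|---|---|
| As written | biopsied, then fail before day 28 | 0.918 − 0.892 = 2.6% (day 21 biopsy); 0.907 − 0.892 = 1.5% (day 24) | 48.8%; 48.3% | 5.8; 5.7 |
| *Did* meant as *did not* | fail before the biopsy | 1 − 0.918 = 8.2%; 1 − 0.907 = 9.3% | 51.8%; 52.5% | 5.6 + 0.69 = 6.3; 5.6 + 0.79 = 6.4 |
| All failures before day 28 (upper bound) | biopsy ignored | 1 − 0.892 = 10.8% | 53.3% | 5.6 + 0.92 = 6.5 |

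In a cohort of 30, d = 2.6% is under one man (0.8) and d = 10.8% is about three (3.2).

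**Dosing days.** The drug is held for 5 days on each side of the biopsy. If the 28 days count dosed days and the biopsy day is also undosed, they end near day 39, where S = 0.853. The rule as written then drops 0.918 − 0.853 = 6.5% (day 21 biopsy) or 0.907 − 0.853 = 5.4% (day 24), and reports 50.9% or 50.3%.

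**OS.** If timed from first dose, 1 − 0.5^(0.920/11.0) = 5.6% die before day 28. Dropping all of them moves the median to 11.0 + 0.92 = 11.9 months. This too is an upper bound.

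**Ceiling.** Analysing 30 men requires 30/(1 − d) enrolled: 31 at d = 2.6% and 34 at d = 10.8%.

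**The case against.** The strongest reply is that the rule as written is narrow. It reaches only men who had the biopsy on days 21–24 and then left before day 28, which on the model shifts 6-month rPFS by about one point. A reader who stops at the first half of the sentence might infer that everyone leaving before day 28 is dropped. The text does not say so, and even the *did not* reading would leave out biopsied men who withdraw. This stands, and it is why the size is given as a range.

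Second, the formula counts every dropped man as a failure. Under Kaplan–Meier, a man who left event-free before day 28 would be censored almost at time zero, so keeping him would barely change the estimate. With first scheduled imaging at 12 weeks, few radiographic progressions would be seen by day 28; losses would be mainly deaths, deterioration and toxicity withdrawals. This stands too. The table shows maxima for each reading, and a fix without follow-up and censoring rules would not remove the bias.

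Third, a reader might infer larger effects from larger early-failure shares. At d = 15%, for example, a true 50% becomes 0.50/0.85 = 58.8%. No such share is in the documents, and 15% exceeds the model's upper bound of 10.8%.

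Fourth, a reader might infer that the rule could turn a null trial into a positive one. Section 12 has no hypothesis test, alpha or success threshold; the aim is estimation, with a half-width near 19 points. Part of any crossing of 50% also comes from rounding 47.6% up.

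Fifth, a reader might infer that OS is also timed from first dose. That origin is documented only for rPFS. Response bias likewise comes mainly from the stricter 3-cycle rule in Section 12.5.2.

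None of this justifies an exclusion based on what happens after treatment starts. It limits how much harm can be claimed.

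**Conclusion.** The concern holds in limited form. Section 12.2 excludes treated men for a post-treatment reason, without naming an endpoint and with no all-treated set to fall back on. Any early failures it removes bias rPFS upward relative to the COMET-1 figure, and OS likewise. The biopsy condition appears inverted and needs the sponsor's clarification.

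Against a true 6-month rPFS of 47.6%, the upward shift is about 0.7–1.3 points as written (48.3–48.8%), 4.2–4.9 points if *did not* was intended (51.8–52.5%), and at most 5.7 points if all failures before day 28 are removed (53.3%). These figures rest on an exponential model, calendar days, and every early failure being dropped; they shrink if dropped men would have been censored event-free. The direction is clear; the size is not settled by the documents. The conflict with the ceiling of 30 is real but administrative.

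**What to change.** - Make all subjects who take at least one dose the primary set for rPFS, OS, response and toxicity. Amend Section 12.5.1 (4 weeks of drug) and Section 12.5.2 (3 cycles) to match; otherwise they would still remove men who stop early.
- Define *withdraws*, separating leaving treatment from leaving the study. Continue follow-up for progression and death after early withdrawal, count both as rPFS events, and censor the rest at the last adequate assessment.
- State that OS is timed from first dose.
- Limit replacement to the paired-biopsy correlative set, meaning subjects without an on-treatment biopsy. Keep every replaced subject in all clinical analyses.
- Restate the ceiling as 30 plus such replacements.
- Present any 28-day evaluable-set result as a sensitivity analysis only.

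The cost is mainly protocol wording, plus follow-up of the few men who leave early and possibly a few extra enrolments for the biopsy set. The estimates may be slightly less favourable. The change should be made before outcome data are reviewed, because it decides who is in the primary analysis.
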